Population	The study population will comprise all adult OAC naïve NVAF patients in Norway who filled a prescription for an OAC (rivaroxaban, apixaban, dabigatran and warfarin) in the study period, defined as from 1 January 2014 to 30 June 2018 (or later depending on availability of data) and followed until outcome of interest, the end of the study period or death. This initiation of an OAC is the index event and requires that there is no previous prescription dispensed for an OAC in the preceding 365 days (counted from the date of the first dispensation backward to the end of OAC supply).
Variables	
Patient demographics (age, gender, migration status, place of birth and date of death), clinical characteristics on outcomes, comorbidities (ICD10 codes and procedure codes with date for admission and discharge) and prescription drugs used both OAC and relevant co-medication (ATC codes with date of dispensation, pack size, strength, number of units and so forth) will be retrieved from the nationwide registries. Risk scores (HAS-BLED and CHA2DS2-VASc) will be calculated.
 
More detailed demographic and clinical data such height, weight, smoking and alcohol use, laboratory values (INR, hemoglobin, s-creatinine) and dosing of OAC will be retrieved from the regional EMR data.

Data sources	De-identified individual level data from three nation-wide registers will form the basis for the analyses, the Norwegian Census Register (FRG), the Norwegian Prescription Database (NorPD) and the Norwegian Patient Register (NPR).

	
Additionally for cohort 2, in the South-East region of Norway, an automated EMR extraction tool will be deployed in order to retrieve additional clinical data that is not present in the nationwide registers.

Study size	
The study population will comprise all adult OAC naïve NVAF patients in Norway who filled a prescription for an OAC (rivaroxaban, apixaban, dabigatran, warfarin) in the study period, defined as from 1 January 2014 to 30 June 2018 (or later depending on availability of data). Based on the information regarding number of patients receiving listed drugs in the country, the sample size for the study will be approximately 70,000 patients.

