9.2.1 Study time frame

For the main analysis, the study population will comprise all adult OAC naïve (no OAC prescription in the previous 365 days, counted from the date of the first dispensation backward to the end of OAC supply) NVAF patients in Norway dispensed a prescription for an OAC (NOAC or warfarin) for the first time in the study period (cohort 1a), defined as from 1 January 2014 to 30 June 2018 (or later depending on availability of data) and followed until endpoint of interest, the end of the study period or death. Patients will be censored at a switch or a discontinuation.

For exploratory analysis, a second study population (cohort 1b) will comprise all adult NVAF patients in Norway that did not receive an OAC (NOAC or warfarin) in the study period, defined as above.

The look-back period will be at least 5 years from the possible earliest index date of NOACs (1 January 2014) going back to 1 January 2009 (available data cut). The minimum follow-up period will be 1 month and the estimated mean follow-up time will be 18 months.

[figure not shown]

Figure 1: Study design

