CHA ₂ DS ₂ VASc	NPR and NorPD	
 - Chronic Heart Failure by NorPD reimbursement codes for heart failure: I50 (ICD10) or K77 (ICPC). 1 point - Hypertension defined by dispensation of at least one anti-hypertensive drug last year prior to index date (see definition above). 1 point - Diabetes defined by dispensation of at least one anti-diabetes drug last year prior to index date (see definition above). 1 point - Age \geq75 years (2 points) or age 64-74 years (1 point) - Previous stroke, TIA or thromboembolism by ICD10 codes (see definition above). 2 points - Peripheral artery disease (ICD10; I739). 1 point - Gender (male=1 point, female=0 point) 
Total score 0 to 9
	Stroke risk score used as co-variate and effect modifier
Charlson co-morbidity index	NPR and NorPD	
 - Age: \leq41 years (0 point), 41-50 years (1 point), 51-60 years (2 points), 61-70 (3 points), \geq71 years (4 points) - Myocardial infarction. 1 point - Congestive Heart Failure. 1 point - Peripheral Vascular Disease. 1 point - TIA or stroke. 1 points - Dementia. 1 point 	Co-morbidity risk score and co-variate

Variable	data source	Definition	Relevance
		
 - COPD. 1 point - Connective Tissue Disease. 1 point - Peptic ulcer and bleeding 1 point - Diabetes. 1 point - Moderate to severe Chronic Kidney Disease (combined CKD and ESRD). 2 points - Leukemia. 2 points - Lymphoma. 2 points - Solid tumour. 2 points - Liver disease. 3 points - Solid tumour with metastasis. 6 points - AIDS. 6 points Total score from 0 to 37	

Table 5: Additional clinical characteristics to be retrieved for the EMR cohort (cohort 2)

Variable	Data source	Operation definition	Relevance
Height	EMR	Height in centimeters from time point closest to the index date	Co-variate
Weight	EMR	Weight in kilogram from time point closest to the index date	Co-variate
Smoking habits	EMR	Smoking habits retrieved as free text search. Converted to pack-years	Co-variate
Alcohol abuse	EMR	Alcohol abuse search as free text	Co-variate
International normalised ratio	EMR	Retrieve all INR measurements from index to the end of study. Calculated INR mean during the study period	Co-variate. Imputation
Blood haemoglobin	EMR	Retrieve all Hb measurements from index to the end of study. Calculated Hb mean during the study period. Identify episodes of more than 20 g/L fall in hemoglobin	Co-variate. Bleeding endpoint

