9.3.2 OAC exposure

New OAC exposure is defined as a single or series of dispensation of an OAC starting in the period from 1 January 2014 to end of study period. The duration of the observation period together with the pack size of each prescription will be used to calculate the length of a patient's OAC exposure. To ensure a minimum of one month follow-up data for all subjects on OAC treatment, inclusion (cut-off index OAC date) will be stopped one month before the end of available follow-up data.

For each dispensation, the OAC days of supply will be computed using information on date of dispensation, the number of packages and the pack-size dispensed. Since NOACs are prescribed in a fixed dose, the number of days of supply strictly corresponds to amount dispensed accounting for a recommended frequency of daily dosing. The NorPD contains information on tablet strength, pack-size and number of packages dispensed, and we assumed, according to the labelling, twice daily dosing for apixaban and dabigatran and once daily dosing for rivaroxaban, e.g. a patient supplied one package of a 100 tablet package of rivaroxaban will have a supply lasting for 100 days, whereas a 100 tablet package of apixaban will provide a supply lasting 50 days.

Computing the warfarin supply is not straightforward as we lack information on both dosing instructions and International Normalised Reference values (INR) in the registries.

Two different methods will be applied to compute the warfarin exposure;

1. EMR data (from cohort 2) holds information on both INR and dosing. Median mg/day of warfarin will be computed in relation to age (in 5-year categories) and gender (females and males). The median mg/day will be used as a basis for computing the warfarin supply in cohort 1.
2. Registry data (from cohort 1) using the length of each time interval in days between dispensation and corresponding dispensed warfarin amount for the time interval will be used to compute the median daily warfarin use for each patient. The calculated median mg/day for all patients using warfarin in the study period, in relation to age group and gender as with method 1, will subsequently be used in the computation of warfarin supply for each dispensation.

Similarly, the same methods will be used to set the end of OAC supply date during the pre-index period to be able to determine if a patient was OAC naïve or not (≥ 365 days without OAC supply prior to index date).

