The duration of dispensation (DoD) will be set as the date of a dispensed prescription plus the estimated duration of that prescription (duration of OAC supply estimated from the dispensed pack-size and strength).

The following rules applies:

1. If the next dispensed prescription was for the same OAC within 30 days after end of DoD there was a continuous treatment
2. If a new dispensed prescription for another OAC occurred within DoD or within 30 days after end of DoD there was a switch in OACs (switching date = date of dispensation)
3. If the next dispensed prescription was for the same OAC more than 30 days after end DoD there was a discontinuation (discontinuation date = date of DoD + 30 days)

A 30-day gap period is included to take into account incomplete adherence to treatment. The figure underneath displays the three different scenarios. In sensitivity analyses the gap period will be varied from 30 days to 0 days, 15 days and 60 days, respectively.

[figure not shown]

Figure 4: Definition of continuation, switch and discontinuation

Patients to be included in the effectiveness and safety analysis should have a supply of OAC covering the event, plus a 30 days grace period for those patients discontinuing their therapy. Any event happening after the date of discontinuation plus 30 days or after a switch in OAC therapy will not be included.

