9.3.3 Estimation of OAC adherence

Proportion of days covered (PDC) will be estimated for each individual from the index medication date and onwards. The PDC is defined as the number of days that the index medication was on hand during the time period divided by the total number of days in the period. For instance if the length of the time period is 100 days and the NOAC supply covers 50 days, the adherence is estimated to 50%.

Likewise, the age- and sex-specific median doses of warfarin (using the two methods described in 9.3.2) will be used to calculate to warfarin supply.

If the OAC supply last longer than the study period the adherence is set to 100%. The proportion of days covered (PDC) will take into account the patient's entire follow-up period, defining end of study period as death, end of study, migration, discontinuation or switch of OAC therapy. In addition to the entire period, adherence will also be estimated at fixed time intervals after OAC index date, i.e. 3 months (90 days), 6 months (180 days), and 9 months (270 days), 1 year (365 days), 2 years (730 days) and 3 years (1095 days).

Consecutive dispensations of the same OAC will be combined and corrected for overlap. For treatment gaps equal or less than 30 days of the previous OAC dispensation it is assumed the patient is on continuous therapy. The length of the gap period will be varied in sensitivity analyses down to 0 and 15 days and up to 60 days.

Some patients switch to another NOAC during follow-up and the day of switch will be defined as the end of the time period. Separately, the PDC for use of any OAC during the study period will be estimated, which accounts for therapy switching during follow-up.

PDC will be estimated as the mean PDC for each OAC as well as grouped into four categories of high adherence (≥ 0.80), moderate adherence (0.50-0.79), low adherence (0.20-0.49) and poor adherence (<0.20). Adherence will also be reported as dichotomized using the conventional PDC of <0.80 or ≥ 0.80 as cutoff. Percentage point differences between OAC user groups will be presented. Analyses of OAC adherence will account for differences in follow-up time and baseline characteristics, such as standard and reduced dosing level.

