9.9 Limitations of the research methods

The strength of the study is that it retrieves data from mandatory and nationwide registries in a public health care system that covers all residents. As a result, the dataset will give us a complete picture of all hospitalizations and prescriptions dispensed nationwide for the entire study period. This complete coverage of data eliminates also selection bias and recall bias that is an apparent problem using other databases being based on selected hospitals, health insurance schemes, or self-reported questionnaires. On top of the nationwide registry data EMR data will give us deeper level phenotypic data such as laboratory values (INR, Hb), weight/height, smoking and alcohol abuse.

This study will measure drug exposure at the level of pharmacy dispensation and will have no information on patient's real OAC intake.

There is also a risk of misclassification related to coding errors of hospital admissions; however, for serious conditions like bleeding and stroke this unlikely a problem. Within the scope of the study a formal validation of the AF diagnosis in NPR will be performed against EMR.

Channeling bias (confounding by indication and severity) pertaining to newer drugs given to poor responding or more fragile patients compared to established drugs is a potential limitation. To mitigate this risk of bias we will use warfarin as reference category and also start the study period 1 January 2014, which will omit the first 6-12 months of NOACs use after reimbursement approval, i.e. when prescription patterns have not yet been established.

Estimates based on the overall population are prone to bias because the decision to give one treatment over the other depends on different baseline characteristics. Therefore any differences in the estimates for some treatment may be caused by the differences in the populations rather by the given treatment.

Due to the separate estimation of the propensity scores the population to compare warfarin vs apixaban may be very different from the population to compare warfarin vs rivaroxaban. Therefore no comparison between the NOACs among each other can be made.

Nonetheless, and although adjustment for a number of important and known baseline characteristics will be performed, some unmeasured and residual confounding related to prescribing behavior or patient characteristics cannot be fully accounted for.

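### In cohort 2, INR is reduced to a single mean up to the end of study, which hides high and low values and is not limited to warfarin users or to time on warfarin

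*Protocol*

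**What the plan says.** Table 5 (Protocol section 9.3.1) lists the extra variables for cohort 2. Its INR row reads "Retrieve all INR measurements from index to the end of study. Calculated INR mean during the study period", and the stated relevance is "Co-variate. Imputation". The haemoglobin row directly below also asks for a mean, but adds a count of falls of more than 20 g/L. The INR row has no such addition. No section names an INR range, a share of values outside a range, or a measure of INR variability.

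Section 9.3.2 says that "EMR data (from cohort 2) holds information on both INR and dosing", but the quantity derived there is a median warfarin dose in mg/day by age group and sex. Section 9.9 presents INR as a gain from the EMR data: "EMR data will give us deeper level phenotypic data such as laboratory values (INR, Hb), weight/height, smoking and alcohol abuse". Section 9.2 gives closer clinical description of patients, including their laboratory results, as the reason for having cohort 2.

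Outcome time is limited to treatment. Section 9.2.1 says "Patients will be censored at a switch or a discontinuation", and section 9.3.2 adds "Any event happening after the date of discontinuation plus 30 days or after a switch in OAC therapy will not be included".

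**The concern.** There are two separate problems with the INR row.

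1. **Scale.** Values that are too high and values that are too low carry different risks, and they offset each other in a mean. Two groups of warfarin users with very different control can have the same mean INR.
2. **Window.** The row collects INRs from index to the end of study for everyone in cohort 2. A patient who stops warfarin or moves to a NOAC no longer contributes outcome time, but later INRs still enter the mean. INRs from patients who started on a NOAC are not excluded either.

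The registries hold no INR, as section 9.3.2 states, so cohort 2 is the only place in this study where the quality of warfarin treatment can be seen. The cohort 2 comparisons of major bleeding will be read against that description. With the planned summary, a reader could not tell good control from poor control with the same average, or a low on-treatment INR from INRs taken after warfarin was stopped.

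**Working it through.** **The plan's own figure.** There is none. The documents give no INR range, mean, SD or sampling frequency, so there is nothing to reproduce. The mismatch in the window follows from the text alone. Its size does not.

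**Step 1: does any passage limit the INR window to treatment?**
- The Abstract (Population) fixes the study period by calendar: "in the study period, defined as from 1 January 2014 to 30 June 2018", or later if data allow.
- Sections 9.2, 9.2.1 and 9.7 censor outcomes at switch or discontinuation, and section 9.3.2 excludes later events.
- The only narrower period is in section 9.3.3: "defining end of study period as death, end of study, migration, discontinuation or switch of OAC therapy". That wording serves the proportion of days covered, and it lists the end of study as an item separate from discontinuation and switch. It therefore does not shorten a window that Table 5 ends at the end of study.

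The INR window can thus run past time at risk.

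**Step 2: what a mean hides.** Assumptions, none from the documents: INR mean 2.5, and an illustrative range of 2 to 3.
- Normal INRs with SD s: share in range = 2Φ(0.5/s) − 1; share above 4 = 1 − Φ(1.5/s).
- Log-normal check with the same mean and SD: v = ln(1 + (s/2.5)²), log-mean = ln 2.5 − v/2, log-SD = √v.

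| SD | In range, normal | In range, log-normal | Above 4, normal |
|---|---|---|---|
| 0.3 | 90% | 91% | 0% |
| 0.8 | 47% | 48% | 3% |
| 1.2 | 32% | 34% | 11% |

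The recorded mean is 2.5 in every row.

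**Step 3: what off-warfarin INRs do to the mean.** Let f be the share of a patient's INRs taken off warfarin. Assume an on-warfarin mean of 2.5 and an off-warfarin INR of 1.1. Then recorded mean = (1 − f) × 2.5 + f × 1.1.
- f = 10%: 2.25 + 0.11 = 2.36
- f = 25%: 1.875 + 0.275 = 2.15
- f = 50%: 1.25 + 0.55 = 1.80

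If the off-warfarin INR is varied from 1.0 to 1.5, the results run from 2.35 to 2.40, from 2.13 to 2.25, and from 1.75 to 2.00. The shift is small when few INRs are taken after stopping and large when many are.

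**The case against.** The strongest reply is that the protocol gives INR two uses, covariate and imputation, and that no objective in section 8 concerns the quality of warfarin control. On that view, a better descriptive summary is a preference. This fails in part, because section 9.2 gives closer description of patients, laboratory results included, as the purpose of cohort 2. The window mismatch also affects a mean used as a covariate or for imputation.

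A second reply is that section 9.7 leaves detailed summaries to the SAP and allows the SAP to modify the protocol. That makes the change easy. It does not make the row an open detail: Table 5 states the summary and its window.

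Several points on the other side stand:
- INR exists only in cohort 2, a pilot that depends on EMR access being granted.
- The sizes in the working rest on assumed values.
- The documents do not say how often INR is recorded in hospital EMRs. If values are sparse or cluster around acute episodes, interpolated time in range may be missing or unrepresentative for many patients.
- Removing the mean altogether would leave the stated covariate and imputation uses without an input.

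A reader might go further and infer that every comparison in the study is compromised. The documents do not support that. Section 8.3 includes exploratory comparisons without a warfarin arm: treated against untreated patients, levels of NOAC adherence, and standard against reduced NOAC dose. The cohorts are analysed separately under section 9.7. The study also compares against warfarin as used in routine care, so imperfect control is part of the comparator and does not invalidate the contrast.

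**Conclusion.** The point holds for cohort 2. The protocol fixes an INR summary that cannot show values too high or too low, over a window that does not match the treatment-limited outcome follow-up and is not confined to warfarin users. The second part rests on the text alone.

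The magnitude is illustrative. Under the stated assumptions, the same mean of 2.5 is compatible with anything from about 90% to about 32% of INRs in range, and INRs off warfarin lower it to between 2.36 and 1.80 when they make up 10% to 50% of the values. The true dilution depends on INR sampling after warfarin is stopped, which the documents do not give.

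The consequence is a potentially misleading description of the warfarin comparator in cohort 2. The nationwide cohort 1 comparison is not directly affected: it has no INR, and the warfarin supply calculation in section 9.3.2 is specified in terms of dose, not INR. No figure stated in the protocol is wrong on this point.

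**What to change.** Amend the INR row of Table 5, and carry the same definition into the SAP:

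1. For description, use warfarin users only, and only INRs taken during continuous warfarin exposure as section 9.3.2 defines it.
2. Report the percentages of INRs below, within and above a range that the sponsor states in advance. The choice of range is the sponsor's.
3. Add interpolated time in range only for patients whose INRs are frequent enough, under a spacing rule fixed beforehand.
4. Report how many patients and how many INRs contribute to each summary, and note that hospital INRs may cluster around acute illness.
5. If a mean is kept for the stated covariate or imputation uses, restrict it to the same on-warfarin window.

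All INR values are already to be retrieved, so the cost is wording and programming, with no new data. Patients with few INRs would contribute only to the percentages. Those percentages share the sampling limits of hospital data, which is why the counts and the caution belong beside them.

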9.3.2 OAC exposure

New OAC exposure is defined as a single or series of dispensation of an OAC starting in the period from 1 January 2014 to end of study period. The duration of the observation period together with the pack size of each prescription will be used to calculate the length of a patient's OAC exposure. To ensure a minimum of one month follow-up data for all subjects on OAC treatment, inclusion (cut-off index OAC date) will be stopped one month before the end of available follow-up data.

For each dispensation, the OAC days of supply will be computed using information on date of dispensation, the number of packages and the pack-size dispensed. Since NOACs are prescribed in a fixed dose, the number of days of supply strictly corresponds to amount dispensed accounting for a recommended frequency of daily dosing. The NorPD contains information on tablet strength, pack-size and number of packages dispensed, and we assumed, according to the labelling, twice daily dosing for apixaban and dabigatran and once daily dosing for rivaroxaban, e.g. a patient supplied one package of a 100 tablet package of rivaroxaban will have a supply lasting for 100 days, whereas a 100 tablet package of apixaban will provide a supply lasting 50 days.

Computing the warfarin supply is not straightforward as we lack information on both dosing instructions and International Normalised Reference values (INR) in the registries.

Two different methods will be applied to compute the warfarin exposure;

1. EMR data (from cohort 2) holds information on both INR and dosing. Median mg/day of warfarin will be computed in relation to age (in 5-year categories) and gender (females and males). The median mg/day will be used as a basis for computing the warfarin supply in cohort 1.
2. Registry data (from cohort 1) using the length of each time interval in days between dispensation and corresponding dispensed warfarin amount for the time interval will be used to compute the median daily warfarin use for each patient. The calculated median mg/day for all patients using warfarin in the study period, in relation to age group and gender as with method 1, will subsequently be used in the computation of warfarin supply for each dispensation.

Similarly, the same methods will be used to set the end of OAC supply date during the pre-index period to be able to determine if a patient was OAC naïve or not (≥ 365 days without OAC supply prior to index date).

The duration of dispensation (DoD) will be set as the date of a dispensed prescription plus the estimated duration of that prescription (duration of OAC supply estimated from the dispensed pack-size and strength).

The following rules applies:

1. If the next dispensed prescription was for the same OAC within 30 days after end of DoD there was a continuous treatment
2. If a new dispensed prescription for another OAC occurred within DoD or within 30 days after end of DoD there was a switch in OACs (switching date = date of dispensation)
3. If the next dispensed prescription was for the same OAC more than 30 days after end DoD there was a discontinuation (discontinuation date = date of DoD + 30 days)

A 30-day gap period is included to take into account incomplete adherence to treatment. The figure underneath displays the three different scenarios. In sensitivity analyses the gap period will be varied from 30 days to 0 days, 15 days and 60 days, respectively.

[figure not shown]

Figure 4: Definition of continuation, switch and discontinuation

Patients to be included in the effectiveness and safety analysis should have a supply of OAC covering the event, plus a 30 days grace period for those patients discontinuing their therapy. Any event happening after the date of discontinuation plus 30 days or after a switch in OAC therapy will not be included.

